- 3- The participant will then be taken to a clinic room, and be shown the consent form. Study design will be explained to them including them receiving the same treatment they would normally but with one injection with 0.5 ml normal saline and one with 0.5 ml 1% lidocaine. They will then be asked if they have any questions and if they choose to consent, they will sign a physical consent form that will then be uploaded into their chart. (30-45 minutes)

2.d Randomization Method and Blinding

Both clinicians and participants will be blinded to the contents of the syringes. Only the nursing staff will know which syringe contains lidocaine and which contains normal saline as they will be drawing up the contents into the syringes, after which they will designate L and R on the syringes and in a log book which will designate which syringe had lidocaine and which had normal saline. This log book will be kept separate from clinicians and participants until study completion. Each participant will have a unique code that will be included in the log book, where the nurse who fills the syringes will state which side, left or right, contained lidocaine and which contained normal saline. This log book will then be used to cross reference injection sites and the survey results during the analysis phase, in a way that allows the data to be de-identified.

2.e Risks and Benefits

Risks

Risks are rare and mainly involve injection site pain, allergic reaction. Some risks, if severe, may cause death.

Likely / Common

Mild

- Pain at injection site (BPG)
- Headache (lidocaine)

- Transient pain (lidocaine)
- Edema (lidocaine)

Less Likely / Less Common

Mild

- Hypersensitivity Rash (BPG)
- Diarrhea (BPG)
- Agitation (lidocaine)
- Anxiety (lidocaine)
- Confusion (lidocaine)
- Dizziness (lidocaine)
- Lethargy (lidocaine)
- Tinnitus (lidocaine)

Rare

Life Threatening

• Hypersensitivity- anaphylaxis (BPG and Lidocaine)

Serious

- Neutropenia (BPG high doses)
- Hyperreflexia (BPG high doses)
- Myoclonus (BPG high doses)
- Seizure (BPG high doses)
- Acute interstitial nephritis (BPG high doses)
- Cardiac Arrhythmia (lidocaine)
- Hypotension (lidocaine)
- Seizure (lidocaine)
- Bronchospasm, dyspnea (lidocaine)

Mild

• Hyperkalemia (BPG)

There is a risk of breach of confidentiality.

Benefits

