The potential benefit to the participant is that they would receive the treatment they normally would but with the potential benefit of less pain in the injection site with 1% lidocaine. As for the benefit to society, this may provide evidence that may change standard clinical practice with respect to how we perform benzathine penicillin G injections in the US and if lidocaine is shown to cause less pain, then it would become standard practice to include 1% lidocaine in each syringe of benzathine penicillin G.

2.f Early Withdrawal of Subjects, Including When and How to Withdraw Subjects

Early withdrawal of subjects will be handled by the principal investigator, with participants having the direct contact of the PI via email or phone, and through stating that they no longer would like to participate in the study. The PI also will have the right

to withdraw someone if upon evaluation of the patient, they meet certain exclusion criteria. All withdrawals will be done immediately and seeing as this study has short term

of participation, withdrawal should not be difficult.

2.g Data Collection and Follow-up for Withdrawn Subjects

Individuals who withdraw from the study will be noted as lost to follow up and no further data will be obtained from them. They will continue to receive standard of care within the outpatient clinical setting.

E3 Study Drug

3.a Description

1% lidocaine solution added to prefilled 1.2 million units Benzathine penicillin G.

3.b Treatment Regimen

0.5ml 1% lidocaine solution added to prefilled 1.2 million units Benzathine Pencillin G syringe

3.c Method for Assigning Subjects to Treatment Groups

Each participant will receive 2x 1.2 million units injection, one with lidocaine and one with normal saline, therefore each participant will serve as both treatment and control group.

3.d Preparation and Administration of Study Drug

Each syringe of BPG is prefilled. A nurse/MA will then add 0.5 ml 1% lidocaine solution to one BPG syringe, and 0.5ml normal saline solution to another BPG syringe. They will randomly syringes to be injected into the left gluteal muscle vs the right gluteal muscle via random assignment program. They will log the assignment with the unique patient code into a log book.

3.e Subject Compliance Monitoring

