- 3- The participant will then be taken to a clinic room and be shown the consent form. Study design will be explained to them including them receiving the same treatment they would normally but with one injection with 0.5 ml normal saline and one with 0.5 ml 1% lidocaine. They will then be asked if they have any questions and if they choose to consent, they will sign a physical consent form that will then be uploaded into their chart. (30-45 minutes)
- 4- Trial staff will then obtain the two injections and administer them one in each gluteal muscle. The patient will then be left for 15 minutes, after which they will fill out a pain score 0-10 for each injection site at 10 minutes post injection. (15-30 minutes)
- 5- Patient will then be informed they will receive an email survey (via RedCap) 24 hours

from trial staff to answer the same pain scale questions at that time. Exit counseling will occur and patient is then free to go. (15 minutes)

F2 Visit 2

Participants will receive an email from trial staff 24 hours after injection site to rate their pain from 0-10 at that time via online survey (RedCap) and to ask if any other pain medication was used in the last 24 hours and if they had any other symptoms/side effects. (5 minutes)

F3 Safety and Adverse Events

3.a Safety Monitoring

Patients will be asked about other side effects/adverse events during the 24 hour follow up. Patients can also contact providers through MyChart and/or through contacting the clinic/trial team.

3.b Medical Monitoring

i Investigator only

The investigator team will be monitoring the survey results for any signs of adverse effects. The monitoring will be ongoing and there will be an internal review of combined data every 6 months.

3.c Definitions of Adverse Events

Any undesirable experience associated with the use of medical product in patient. Common adverse events are listed above.

3.d Classification of Events

i Relationship

10 minutes after injection vs. 24 hours after injection

ii Severity

Mild, Moderate, or life threatening

iii Expectedness

Rare, other than injection site pain which is common

3.e Data Collection Procedures for Adverse Events

Adverse events will be asked about in the survey given 24 hours post injection.

3.f Reporting Procedures

Participants will report adverse events via a RedCap survey emailed 24 hours post injection. Other adverse events can be reported to PI or to clinic staff.

3.g Adverse Event Reporting Period

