Adverse events can be reported within 7 days post injection with participants having the ability to call for up to 7 days.

3.h Post-study Adverse Event

Any adverse event post study or the time listed above should be reported to the PI.

F4 Study Outcome Measurements and Ascertainment

The primary outcome measure will be pain rating scores from 0 (least pain) to 10 (most pain) at 10 minutes after injection in each injection site, as well as 24 hours after injection.

Secondary outcome measures will include adverse effects of lidocaine or benzathine penicillin G., such as allergic reactions or injection site reactions.

F5 Rationale for the Selection of Outcome Measures

Injection site pain is the most common adverse effect of Benzathine Penicillin G (BPG) intramuscular injections. For this reason, rating pain scales from 0-1 10 minutes and 24 hours after injection will allow us to measure immediate and longer term pain after injection, with and without lidocaine added to prefilled BPG syringes.

G Statistical Plan

G1 Sample Size Determination and Power

A sample size of 46 patients (92 injections) will be required to detect a clinically significant reduction in pain and discomfort associated with the injection of Bicillin, with a power of 80% and a significance level of 0.05.

G2 Interim Monitoring and Early Stopping

As this is a short term study with small population, it is not expected to stop early. Interim monitoring for adverse effects will occur at 6 months or after 24 participants have participated, whichever occurs first.

G3 Analysis Plan

Pain scores will be collected by trained study personnel. Data will be entered into a secure database and analyzed using statistical software. Descriptive statistics will be used to summarize the data, and t-tests or chi-squared tests will be used to compare pain scores and adverse effects between the treatment and control groups. They will also see if there any use of pain medications through descriptive statistics. Demographic data will also be collected.

G4 Statistical Methods

Descriptive statistics will be used to summarize the data, and t-tests or chi-squared tests will be used to compare pain scores and adverse effects between the treatment and control groups.

G5 Missing Outcome Data

Missing outcome data on follow up will be noted and statistical analysis will be performed on intention to treat model.

G6 Unblinding Procedures

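### The order of the two injections is neither set nor logged, so any first-versus-second effect on pain adds avoidable noise to the within-person comparison

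*Protocol*

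**What the plan says.** Section E3 3.d assigns the syringes to sides by a program (a verb is missing in the text): "They will randomly syringes to be injected into the left gluteal muscle vs the right gluteal muscle via random assignment program". Section E2 2.d describes the log book, in which "the nurse who fills the syringes will state which side, left or right, contained lidocaine and which contained normal saline". Under E3 3.g the two syringes look alike apart from an L or R label. So side is the only thing randomised, labelled and logged.

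At the bedside, F1 step 4 says only that trial staff fetch both syringes and then "administer them one in each gluteal muscle". No section fixes a first side, randomises order, or provides a field for order or for the time of each injection. The same step has each site scored at 10 minutes after injection, without saying from which of the two injections the time runs.

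Section A1 states that the injecting assistant and the participant are both blinded, and E3 3.c makes each participant their own control. On size, G1 says "A sample size of 46 patients (92 injections) will be required" to "detect a clinically significant reduction in pain and discomfort", "with a power of 80% and a significance level of 0.05". It gives no difference in points, no SD and no correlation. G3 and G4 name t-tests or chi-squared tests and no side or order term.

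**The concern.** The strength of this design is that each person supplies both ratings, so variation between people drops out. What remains is anything that differs between the two sites within a person. Order is an obvious candidate. Unless the two injections are simultaneous, one site is injected earlier and so has had longer to settle when it is rated, and the second is felt against the memory of the first.

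If lidocaine goes first in some participants and second in others, an order effect is added to some differences and subtracted from others. It averages out in expectation but widens the spread. An analysis plan can add a term for a recorded variable. It cannot recover one that was never written down. That is why this belongs in the Protocol and its log book, before enrolment starts. At stake is power in a trial of 46 people planned at 80%.

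**Working it through.** **The plan's own figure.** The 46 in G1 cannot be reproduced, because no effect size or SD is given. It can only be solved backwards. For a paired, two-sided test at 0.05 with 80% power:

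- normal approximation: d = (1.960 + 0.842)/√46 = 0.413
- noncentral t with 45 degrees of freedom: d = 0.422

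Here d is the true mean difference divided by the SD of the within-person difference. Two-sided testing is an assumption, since G1 does not state sidedness.

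**Model.** For participant i, let the lidocaine-minus-saline difference be

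D_i = τ + s_i·δ + e_i,

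where τ is the lidocaine effect, δ is the first-minus-second difference in rating, s_i is +1 if lidocaine was given first and −1 if second, and e_i has standard deviation SD. Side is randomised and the injector is blinded, so s_i takes either sign with equal probability, whatever habit the injector has. Therefore:

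- the mean of D_i is τ, so there is no bias
- the variance of D_i is SD²·(1 + r²), with r = δ/SD
- the noncentrality of the unadjusted paired t-test is √46·0.422/√(1 + r²) = 2.863/√(1 + r²)

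**Inputs that the Protocol does not give.** The size of δ is unknown, so r is varied as an assumption. SD is taken as the spread without order variance, and power is set to 80% at r = 0.

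| r = δ/SD | Variance factor 1 + r² | Noncentrality | Power, order not modelled | N to restore 80% (46·(1 + r²)) |
|---|---|---|---|---|
| 0 | 1.00 | 2.863 | 80.0% | 46 |
| 0.1 | 1.01 | 2.849 | 79.6% | 47 |
| 0.25 | 1.0625 | 2.778 | 77.6% | 49 |
| 0.5 | 1.25 | 2.561 | 70.8% | 58 |

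With order recorded, balanced 23 to 23 and fitted as a term (44 degrees of freedom), power is 80.0% whatever the value of δ.

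**Check by simulation** (20,000 trials per setting, sign of s_i by simple randomisation):

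| r | Type I error, unadjusted | Power, unadjusted | Power, order fitted |
|---|---|---|---|
| 0 | 4.7% | 80.5% | 79.6% |
| 0.25 | 5.2% | 78.0% | 79.5% |
| 0.5 | 4.9% | 70.9% | 79.3% |

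The simulation agrees with the formula. Type I error stays near 5%, so the cost is precision only.

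**The case against.** The strongest reply is that nothing here threatens validity and that the harm rests on assumed values. Much of that stands. The documents contain no evidence of an order effect. Up to 0.25 SD the loss is under 3 percentage points. The 0.5 SD case needs an order effect larger than the lidocaine effect the trial is sized to detect (0.5 against 0.422 SD). If the unstated planning SD came from data in which order was also uncontrolled, the 80% already includes this noise, and modelling order would be a gain and not the repair of a loss. The interval between injections is not stated either. A short interval would make the timing difference small at 10 minutes and negligible at 24 hours.

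It can also be said that order might be recoverable. E2 2.c has treatment documented in the chart, and if staff always start on the same side, the logged side identifies order. Both are possible, but the Protocol says neither what the chart entry contains nor that one side goes first, so neither can be relied on.

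A reader might infer two stronger things that the documents do not support:

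- **That the side split will be unbalanced.** E3 3.d mentions only a random assignment program. Whether it uses blocks is not described and may sit in a randomisation plan. Even under simple randomisation, a split of 28 to 18 or worse has probability 0.18, and with side fitted a 28 to 18 split still leaves power at 78.0%.
- **That a left-right effect could not be adjusted for later.** Side is logged and linked to the ratings at analysis, so it can be.

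**Conclusion.** The point holds as a modest matter of precision and data capture, not as an error in validity. The Protocol randomises and logs side but does not set, randomise or provide for recording order. The estimate stays unbiased and the test keeps its level. The possible loss runs from negligible (79.6% power at 0.1 SD) through small (77.6% at 0.25 SD) to material only if the order effect is large (70.8% at 0.5 SD). It probably matters more for the 10-minute rating than for the 24-hour one.

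These figures assume 46 complete pairs, a two-sided paired t-test, 80% power when there is no order effect, and an order effect that is the same for everyone. The Protocol supplies no SD, effect size or order effect to narrow the range. The case for acting is that the change costs almost nothing and an unlogged order may be impossible to reconstruct afterwards.

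**What to change.** 1. In E3 3.d, have the random assignment program allocate the first-injected side together with the lidocaine side, in blocks over the four combinations if feasible. Lidocaine-first and lidocaine-left are then balanced and unrelated to each other. With 46 participants that is 11 blocks of four and two left over.
2. In E3 3.g, add first or second to the L and R labels. In F1 step 4, have the injector follow the label.
3. In E2 2.d, add log-book fields for the order actually given and the time of each injection.
4. In G3 and G4, analyse the paired lidocaine-minus-saline differences with order and the already logged side as terms coded +1 and −1, so that the intercept is the lidocaine effect. Balance without these terms would not remove the variance from a simple paired t-test.

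The cost is a slightly longer list, one more word on each label, a few log fields and at most two degrees of freedom. Some assignments could be guessed near the end of a block, but only by the preparer, who already knows the contents. If randomising order is unwelcome, the minimum is to log it, or to fix one first side for everyone so that the logged side stands for both.

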The purpose of the study is to test the question of: Does the addition of 0.5ml 1% lidocaine compared to 0.5 ml normal saline solution to 1.2 million units of benzathine penicillin G affect the pain experienced by individuals being treated for Treponema pallidum (syphilis) infections at 10 minutes and 24 hours post injection?

B Background

B1 Prior Literature and Studies, and Rationale for this Study

There is evidence to suggest that lidocaine can help reduce the pain associated with intramuscular injections of benzathine penicillin G or bicillin, used to treat syphilis

infections. A study published in the Journal of Pediatric Infectious Diseases in 1998 found that the use of lidocaine as a diluent of BPG significantly reduced the pain of injection. Another study by Estrada et al in 2019 looked at the addition of 1% mepivicaine as diluent for PGB vs PGB alone and showed that mepivicaine significantly decreased pain experienced by participants. Per the IUSTI European Guidelines for Syphilis management, lidocaine is used as a diluent for benzathine penicillin G since 1998. No studies have been performed thus far looking at prefilled benzathine penicillin G syringes and the possibility of inserting lidocaine to the injection to decrease the pain experienced by individuals being treated for syphilis infections, instead of using lidocaine as a diluent which is not possible for the BPG formulations present here in the US. in the US.

C Study Objectives

C1 Primary Aim

To see if there is any benefit of adding 0.5 ml 1% lidocaine to prepackaged Benzathine Penicillin G, with respect to pain, compared to standard of care, in the treatment of Treponema pallidum infections, both 10 minutes and 24 hours after injection.

C2 Secondary Aim

To see if there are any adverse effects of adding 0.5 ml 1% lidocaine to prepackaged Benzathine Penicillin G and to assess use of other pain medications 24 hours post injection.

D Investigational Agent

D1 Preclinical Data

1% lidocaine has been added as a solvent for BPG in other countries around the world.

D2 Clinical Data to Date

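### Adverse-event Relationship is defined by time since injection instead of causality, does not fit the collection and reporting rules, and leaves the planned lidocaine-versus-saline safety comparison weakly supported

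*Protocol*

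**What the plan says.** Protocol C2 sets the safety part of the secondary aim: "To see if there are any adverse effects of adding 0.5 ml 1% lidocaine to prepackaged Benzathine Penicillin G". F4 names adverse effects of either lidocaine or BPG as the secondary outcome.

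F3 3.d lists three ways to classify an event: relationship, severity and expectedness. The whole entry under Relationship is "10 minutes after injection vs. 24 hours after injection".

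On collection, F3 3.e says "Adverse events will be asked about in the survey given 24 hours post injection", and 3.f says "Participants will report adverse events via a RedCap survey emailed 24 hours post injection". F2 describes the question in that survey as asking "if they had any other symptoms/side effects". At the visit, F1 step 4 says that "they will fill out a pain score 0-10 for each injection site at 10 minutes post injection" and mentions no other question. Unsolicited routes are open: 3.f adds "Other adverse events can be reported to PI or to clinic staff", and 3.g says "Adverse events can be reported within 7 days post injection with participants having the ability to call for up to 7 days".

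G3 and G4 compare both pain scores and adverse effects between treatment and control groups by t-tests or chi-squared tests. E3 3.c makes each participant a member of both groups.

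**The concern.** A relationship field exists to record whether an event is judged to be due to a product or procedure. Here it records when the event was noticed or asked about. The protocol needs the causal judgement: C2 and F4 speak of effects of an agent, the risk list in E2 2.e assigns each risk to BPG or lidocaine, and F3 3.c defines an adverse event by its association with a medical product. No rule says how association is to be judged.

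This is not a detail left to an analysis plan. The protocol has the heading and puts the wrong content under it. The time classes also do not match the protocol's own collection and reporting rules. At stake are the attribution of individual events, the recording of onset, and the adverse-effect comparison in G3 and G4.

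**Working it through.** The plan gives no figure on this point, so the check sets the sections side by side.

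| Question | Where | What is provided |
|---|---|---|
| How is relationship classified? | F3 3.d.i | 10 minutes or 24 hours |
| Is causality rated elsewhere? | whole protocol | no |
| When are general adverse events solicited? | F2; F3 3.a, 3.e, 3.f | 24-hour survey only |
| What is collected at 10 minutes? | F1 step 4 | 0-10 pain score per site |
| How long are reports accepted? | F3 3.g | 7 days |
| What is recorded by side? | F1 step 4, F4 | pain |
| How are adverse effects analysed? | G3, G4 | treatment versus control |

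**Step 1: label against content.** Both entries under Relationship are times. An event coded exactly as written carries no judgement on lidocaine, BPG or the injection.

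**Step 2: the 10-minute class.** The only scheduled item at 10 minutes is the pain score. An early event other than pain would reach the data through recall in the 24-hour survey or an unsolicited report. No onset-time field is described that would place such an event in the 10-minute class.

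**Step 3: coverage.** Even if the second label is read generously as everything up to 24 hours, it covers 1 of the 7 reporting days. The other 7 − 1 = 6 days have no class, so an event on day 3 cannot be coded.

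**Step 4: the planned comparison.** There are 46 participants and 92 injections, hence 46 lidocaine and 46 saline injections in the same people.

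- *Systemic events.* Suppose s participants have one. All of them received both solutions, so the count is s/46 under lidocaine and s/46 under saline. The difference is s/46 − s/46 = 0 whatever lidocaine does.
- *Local reactions.* The side can be linked to the solution through the log book (E2 2.d), and sides are assigned by a random assignment program (E3 3.d). The comparison works if the side of the reaction is recorded. The protocol describes recording by side only for pain; the F2 wording on symptoms is general.

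Neither a time label nor a causality rating changes the result for systemic events. That limit comes from the within-participant design.

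**The case against.** Three stronger readings are tempting, and the documents support none of them.

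- *A reader might infer that the safety aim cannot be answered.* The G3 and G4 comparison does not use the Relationship field. With randomized sides and a log book, local reactions can be attributed without investigator causality if side is recorded, and the survey form is not shown, so it may be. Frequencies can be described in any case: with no events in 46 participants, the one-sided 95% upper limit is 1 − 0.05^(1/46) = 0.063, or 6.3%. C2 also covers use of other pain medication, which this point does not touch.
- *A reader might infer that nothing is collected at 10 minutes.* Pain is scored for each site then, and F5 calls injection-site pain the most common adverse effect of BPG injections. The 24-hour question is not restricted to symptoms still present, so early events can be recalled.
- *A reader might infer that participants who ignore the email contribute no safety data.* E3 3.e provides a second email at 48 hours, and events can be reported through MyChart, the clinic, the trial team or the investigator. Only solicited data would be lost. Any count of such participants would need an assumed non-response rate, and the loss would be the same under a perfect causality scale.

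It is also fair to say that no section plans to tabulate the Relationship field, so a misleading table is possible but not planned.

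These objections limit the consequence. They do not remove the wrong content in 3.d.i, its mismatch with 3.e to 3.g, or the absence of any stated recording by side for reactions other than pain.

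**Conclusion.** The point holds as a mis-specified classification that conflicts with the protocol's own collection and reporting rules. As written, no event receives a causality rating, the 10-minute class has no scheduled general adverse-event question, and 6 of the 7 reporting days have no class. The adverse-effect comparison in G3 and G4 is informative only for local reactions recorded by side, and such recording is described for pain alone. Event-level attribution, onset timing and that comparison are weakened but not made impossible.

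The primary pain outcome is not affected. The conclusion rests on the protocol text and needs no assumed rate. It does depend on the unseen survey form not already capturing side and onset; if it does, what remains is to correct 3.d.i, state those fields in the protocol, and restrict the comparison. The correction should be made because it is specific and cheap.

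**What to change.** 1. Replace the content of F3 3.d.i with a causality rating (for example unrelated, possibly, probably or definitely related) to BPG, to the added solution and to the injection procedure, made while the rater is still blinded to side.
2. Record onset time as a separate field.
3. Record the location of each event as left, right, both or systemic.
4. Add one general adverse-event question to the on-site 10-minute form.
5. Reconcile 3.d with 3.e, 3.f and 3.g so that the classes, the collection times and the 7-day period agree.
6. In G3 and G4, limit the lidocaine-versus-saline comparison to site-specific reactions and describe systemic events for the whole cohort. A causality rating cannot separate systemic events by solution when everyone receives both.

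The cost is a few REDCap fields, one extra question while the participant is still in clinic, and a short wording change to the protocol.

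### The adverse-event severity scale has no grade for a severe or fatal event, and the expectedness line gives a frequency that contradicts the protocol's own risk list

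*Protocol*

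**What the plan says.** Protocol F3, 3.d (Classification of Events) fixes two rules that matter here:

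- Severity (ii): "Mild, Moderate, or life threatening".
- Expectedness (iii): "Rare, other than injection site pain which is common".

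The risk list is in Protocol E2, 2.e (Risks and Benefits). It warns at the outset: "Some risks, if severe, may cause death". It then sorts risks into three frequency tiers, headed "Likely / Common", "Less Likely / Less Common" and rare. Within the tiers it uses three classes: mild, serious and life threatening.

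Adverse effects are the subject of the secondary aim (C2, together with pain-medication use) and the secondary outcome (F4). They are also the stated subject of the interim monitoring in G2. F3, 3.b leaves safety monitoring to the investigator team alone.

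**The concern.** A severity scale has to hold every event that can occur. This one stops at moderate and resumes at life threatening, and it ends before death. Staff who meet a severe event that does not threaten life must move it down or up, and no rule says which. A fatal event would have to be recorded as something less.

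Expectedness is normally a yes/no judgment against a reference list. Here it is a statement about how often events occur, so it cannot be used to decide whether a given event was expected. As a statement about frequency, it disagrees with the list in the same protocol.

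At stake is whether events are recorded consistently in a trial where one team records, monitors and reports them.

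**Working it through.** The protocol gives no figure on this point, so the check is a comparison of F3, 3.d with E2, 2.e, plus counts.

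**Severity.**

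| Level or class | In F3, 3.d.ii | In E2, 2.e |
|---|---|---|
| Mild | yes | yes |
| Moderate | yes | not used |
| Severe | no | only in the opening warning |
| Serious | no | yes, 9 entries |
| Life threatening | yes | yes, 1 entry |
| Fatal | no | only in the opening warning |

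The two vocabularies share only mild and life threatening. The protocol recognises both severe and fatal outcomes in 2.e, but 3.d.ii has a grade for neither. The gap follows from the scale itself and does not depend on how the serious class is read.

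**Expectedness.** Entries in 2.e by frequency tier:

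- Likely or common: 4 (BPG injection-site pain; headache, transient pain and edema for lidocaine).
- Less common: 8 (rash, diarrhea, agitation, anxiety, confusion, dizziness, lethargy, tinnitus).
- Rare: 1 life threatening + 9 serious + 1 mild = 11.
- Total: 4 + 8 + 11 = 23.

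The line in 3.d.iii exempts injection-site pain and calls everything else rare:

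- If only the BPG entry counts as site pain, 23 − 1 = 22 entries are called rare. The list agrees for 11 and disagrees for 22 − 11 = 11 (3 common, 8 less common).
- If lidocaine transient pain is also read as site pain, 23 − 2 = 21 are called rare, and the list disagrees for 21 − 11 = 10 (2 common, 8 less common).

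Headache is the clearest conflict, because it cannot be read as site pain on any reading. F3, 3.c, just above, also refers back to common adverse events in the plural, which does not fit a rule that leaves only one.

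**Where the classification is used.** F4 defines the secondary outcome by type of adverse effect, with allergic and injection-site reactions as examples. G3 and G4 compare adverse effects between treatment and control. Neither severity grade nor expectedness enters a stated outcome, test or interim trigger. F3, 3.f to 3.h attach no reporting step to expectedness.

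**The case against.** The strongest case against is that nothing in the protocol turns on these two lines, so this is a matter of wording. Several parts of that case stand.

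- A reader might infer that the safety outcome will be distorted because events are misgraded. The protocol does not support this. Outcome and tests rest on the occurrence of adverse effects, not on grade, and no tabulation by grade is described. A statistical analysis plan that is not at hand might use grade; that can be neither confirmed nor excluded.
- A reader might infer that the expectedness line also misgrades severity. It cannot, because these are separate attributes. Nor does the line say unexpected; it says rare. It can mislead a judgment of expectedness, but no documented action follows from that judgment.
- A reader might count the 9 serious entries as 9 events that will be misgraded. Seriousness is not severity, all 9 are in the rare tier, and 5 of them are tied to high doses of BPG. The count shows that the vocabularies differ, not how many errors to expect.
- A reader might express the harm as a change in a severe-event rate among the 46 patients. The protocol defines no such rate, and regrading one event would move a proportion in any trial of that size. It shows nothing about this scale.
- Edema has no stated location and could be a local reaction. If it were exempted too, the disagreements would fall to 1 common + 8 less common = 9. But 3.d.iii exempts pain only, and edema is not pain.
- The opening of 2.e itself calls the risks rare, so 3.d.iii may only repeat that summary. This explains the conflict without removing it: the summary disagrees with the tiers beneath it as well.

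What the objection does not answer is that both lines are written rules. Applied as they stand, they record a severe or fatal event in the wrong grade and call a listed common event rare.

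**Conclusion.** The point holds for classification. The severity scale lacks a severe and a fatal level and does not match the classes in 2.e. The expectedness line is a frequency, and it contradicts 2.e for 10 or 11 of 23 entries, with headache the unambiguous case. The consequence is confined to how adverse events are classified in safety monitoring and reporting. No effect on the between-group comparison of adverse effects is shown, and no numerical effect is claimed.

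This rests on two assumptions: that F3, 3.d is meant to be applied to each recorded event, and that no other document replaces its scale. It is worth correcting because the correction is nearly free, whereas regrading after events are recorded would rely on retrospective judgment.

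**What to change.** - In F3, 3.d.ii, use one set of severity levels that includes severe and fatal, for example mild, moderate, severe, life threatening, fatal. Use the same terms wherever 2.e describes severity.
- Record seriousness as a separate yes/no item.
- In F3, 3.d.iii, define an event as expected if it is listed in 2.e for BPG or lidocaine, and otherwise as unexpected.
- Reconcile the frequency wording of 3.d.iii, the opening sentence of 2.e and the tiers of 2.e.

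The cost is a few lines of protocol text. F3, 3.e says only that the 24-hour survey asks about adverse events, so extra REDCap answer options are needed only if grade is captured there. The change touches recording only: no dose, treatment, outcome or test is altered.
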